3.2. Treatment groups

Patients who have signed an informed consent statement and who meet the eligibility criteria will be randomly assigned to one of three groups for 96 weeks of treatment:

Group 1:	Pioglitazone (30 mg q.d.) and vitamin E-placebo (q.d)
Group 2:	Vitamin E (800 IU, natural form, q.d.) and pioglitazone-placebo (q.d.)
Group 3:	Pioglitazone-placebo (q.d.) and vitamin E-placebo (q.d.)

The randomization scheme will assign patients in randomly permuted blocks of assignments stratified by clinical center; block size will be determined randomly. This scheme will ensure that the three groups will be balanced by calendar time of enrollment (to minimize secular effects) and by clinic (to minimize clinic-specific effects of differences in patient populations and management).

The randomization plan will be prepared and administered centrally by the Data Coordinating Center (DCC) but will not require real time interaction with a DCC staff member. Requests for randomizations will be made by the clinics using a web-based application. An assignment will be issued only if the database shows that the patient is eligible, has signed the consent statement, and has had all required baseline data keyed to the database.

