6.2. Outcome measures

Primary outcome measure:

The primary outcome measure requires improvement in NASH activity after 96 weeks of treatment as determined by liver biopsies pre- and post-treatment. The measure is derived from changes from baseline to the end of treatment in the NASH CRN NAFLD/NASH activity score (NAS). The NAS ranges from 0 to 8 (highest activity) and is calculated as the sum of three components of the standardized histologic feature scoring system for liver biopsies:

NAS	=	Steatosis score $(0-3) +$
		Lobular inflammation score $(0-3) +$
		Hepatocyte ballooning score (0-2)

As noted earlier, a NAS of 5 or greater with each subscore at least 1 or a NAS of 4 with each subscore at least 1 and a finding of definite steatohepatitis by at least two of three NASH CRN pathologists is a requirement for enrollment into the trial.

38

The definition of improvement after treatment as the primary outcome measure requires the following three conditions:

- No worsening of the fibrosis feature score
- Improvement by at least 1 point in the hepatocyte ballooning feature score
 - Either: (1) Improvement in NAS by 2 or more points spread across at least two of the NAS components, OR
 - (2) Post-treatment NAS is 3 points or less

Secondary outcome measures:

- Change in NAS after 96 weeks of treatment compared to baseline NAS. Mean changes in NAS will be compared.
- Changes in fibrosis, steatosis, lobular inflammation, cellular ballooning and other specific features from the histologic scoring system after 96 weeks of treatment compared to baseline. Improvement in specific features will be defined as any improvement in the score. Mean changes will also be compared.
- Change in serum aminotransferase levels after 96 weeks of treatment compared to baseline. A biochemical response is considered a fall of ALT levels into the normal range. Patients are not required to have abnormal levels of aminotransferases in order to enter this trial as long as they meet histological and other clinical criteria. Therefore, patients with normal levels of transaminases may be enrolled. If an adequate number of such patients are enrolled, a subgroup analysis will be performed.
- Change in anthropometric measurements (weight, BMI, waist-to-hip ratio, waist circumference, triceps skin fold thickness and total body fat) after 96 weeks of treatment compared to baseline.

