In general, analyses for outcomes related to other secondary hypotheses will be conducted in two ways. Improvement will be analyzed both as a binary outcome (improved vs. not improved) and also in terms of the numerical change in the outcome. Binary outcomes will be compared using the uncorrected χ^2 test for 2x2 table. Numerical changes will be analyzed by descriptively comparing the between-treatment group differences in mean and median changes; P-values will be derived from Wilcoxon rank sum tests for comparison of the distribution of changes in each group. If concerns about confounding arise, logistic regression models for improvement outcomes and linear regression models for numerical change outcomes will be used to correct for the confounding. Analyses for secondary hypotheses will generally involve three separate analyses, one for each treatment group comparison: pioglitazone vs. placebo, vitamin E vs. placebo, and pioglitazone vs. vitamin E. No adjustments for multiple comparisons will be applied to the secondary hypotheses; however, any significant findings must be interpreted taking into account the strength of the finding and its biologic plausibility.

Other questions to be addressed:

A series of other questions of interest were listed in Section 6.1. Analyses related to these questions will involve a mix of appropriate exploratory and confirmatory analyses, similar, but not limited to those described for the primary and secondary hypotheses.

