6.5. Justification of sample size

The planned sample size for the PIVENS trial is 240 patients with equal allocation to each of the three treatment groups (80 per group).

We based the sample size estimates on a two-group, binomial comparison of the proportions of patients satisfying the primary outcome, improvement in the histologic activity score (defined in Section 6.2) over the course of treatment. Since PIVENS is a three group trial with two primary hypotheses, we assume that the two primary comparisons, pioglitazone vs. placebo and vitamin E vs. placebo, require the same sample size and reduce the type I error from 0.05 to 0.025 (Bonferroni correction). Expected proportions improved were approximated using pilot data from a 48-week pioglitazone study ([name] and [name], personal communication) and from the placebo group in a two-year randomized trial of Urso vs. placebo ([name], personal communication). Currently, there are no available data to estimate the response in vitamin E, which is assumed, for purposes of planning the trial, to be the same as for pioglitazone.

41

The sample calculations were performed using the nQuery Advisor 5.0 (67) software using the formula:

$$n = \frac{\left[z_{1-\alpha/2}\sqrt{2\overline{\pi}(1-\overline{\pi})} + z_{1-\beta}\sqrt{\pi_1(1-\pi_1) + \pi_2(1-\pi_2)}\right]^2}{(\pi_1 - \pi_2)^2}$$

where,

- n = sample size per group
- π_1 = expected proportion improved in placebo group (assumed=0.14)
- π_2 = expected proportion improved in pioglitazone or vitamin E group (0.40)
- $\overline{\boldsymbol{\pi}}$ = average of π_1 and π_2
- α = Two-sided type I error (0.025, Bonferroni corrected for two comparisons)
- β = Type II error (0.10; i.e., 90% power)

The number per group, using the above formula is 71. Inflating this number by the 10% expected missing data rate yields approximately 80 patients per group, or a total of 240 for the trial.

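### The secondary tests leave out the clinic strata and do not adjust for baseline: they are valid but lose precision that the trial could have at no cost.

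*Protocol*

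**What the plan says.** Section 3.2 assigns treatment in "randomly permuted blocks of assignments stratified by clinical center". Section 6.3 gives this stratification as the reason for using a Mantel-Haenszel test on the primary outcome.

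For the other secondary outcomes, section 6.3 fixes different tests in general terms. For binary outcomes: "Binary outcomes will be compared using the uncorrected" chi-square test for a 2x2 table. For numerical outcomes, mean and median changes are described and "P-values will be derived from Wilcoxon rank sum tests for comparison of the distribution of changes in each group". Logistic or linear regression follows only where confounding becomes a concern; no covariates and no criterion are named. No multiplicity adjustment is applied, and significant secondary findings are to be read with regard to their strength and plausibility.

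Section 6.2 sets two response rules:
- For ALT: "A biochemical response is considered a fall of ALT levels into the normal range". The same bullet allows patients with normal transaminases to enrol and foresees a subgroup analysis if enough do.
- For histologic features: "Improvement in specific features will be defined as any improvement in the score".

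Neither rule states a denominator.

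**The concern.** The protocol's own argument for stratifying the primary test applies equally to the secondary outcomes, which come from the same randomization. It then names secondary tests without a clinic term and does not say why.

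The larger loss is at baseline. A raw change score subtracts the whole baseline value, whatever its correlation with the week-96 value. That adds noise whenever the correlation is below 1 (equal variances assumed). A regression that starts only when confounding is suspected is aimed at bias, which randomization already handles, and leaves the noise in place. With no covariates or criterion fixed, it can also be called on after the results are seen. No secondary outcome entered the sample size in section 6.5, so their power is whatever 80 patients per group happen to give.

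The lesser concern is definitional. A patient whose ALT is already normal cannot fall into the normal range, and a feature scored 0 cannot improve. Without a stated denominator, one outcome can be reported as several different rates.

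**Working it through.** **Inputs from the protocol.** "Two-sided type I error (0.025, Bonferroni corrected for two comparisons"); "Type II error (0.10; i.e., 90% power"); "expected proportion improved in placebo group (assumed=0.14"); active-group proportion 0.40; 80 per group; 10% missing (section 6.5). Eight centers averaging 30 patients (section 4.1), so about 10 per arm per center and 9 evaluable, or 8 × 9 = 72 per arm.

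**The plan's own figure.** With mean proportion 0.27:

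n = [2.2414·√(2·0.27·0.73) + 1.2816·√(0.14·0.86 + 0.40·0.60)]² / 0.26² = (1.407 + 0.769)² / 0.0676 = 70.08, rounded up to 71.

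71/0.9 = 78.9, so 79, stated as about 80. The figure reproduces, and nothing below changes it.

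**Step 1: baseline adjustment.** With equal variance s² at both times and correlation r:
- the change score has variance 2s²(1−r);
- ANCOVA has variance s²(1−r²);
- the ratio is (1+r)/2.

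The protocol gives no r, so a range is assumed. The last column is Φ[(1.960 + 0.842)·√ratio − 1.960], at two-sided 0.05.

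| r (assumed) | Variance ratio, ANCOVA/change | N needed by change score, relative to ANCOVA | Change-score power where ANCOVA has 80% |
|---|---|---|---|
| 0.2 | 0.60 | 1.67 | 58% |
| 0.3 | 0.65 | 1.54 | 62% |
| 0.5 | 0.75 | 1.33 | 68% |
| 0.7 | 0.85 | 1.18 | 73% |
| 0.8 | 0.90 | 1.11 | 76% |

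This is a linear-model proxy. The planned test is a rank test on changes, some of them in short ordinal scores, so the exact gain will differ.

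**Step 2: clinic strata.** Simulation with 8 clinics and 9 evaluable patients per arm in each, at two-sided 0.05. Clinic variation is assumed, since the protocol gives none.

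Binary outcome, 20% vs 40% for power and 25% in both arms for type I error, 20,000 runs:

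| Clinic SD (logit) | Power, chi-square | Power, Mantel-Haenszel | Type I error, chi-square |
|---|---|---|---|
| 0 | 76% | 76% | 5.2% |
| 0.3 | 75% | 76% | 5.1% |
| 0.6 | 72% | 74% | 4.7% |
| 1.0 | 65% | 70% | 3.5% |

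Numerical outcome, effect 0.45 SD, 4,000 runs, Wilcoxon against its stratified form (van Elteren):

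| Intraclass correlation | Power, Wilcoxon | Power, van Elteren | Type I error, Wilcoxon |
|---|---|---|---|
| 0 | 74% | 72% | 5.7% |
| 0.1 | 75% | 77% | 4.1% |
| 0.2 | 78% | 82% | 3.0% |

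Ignoring the strata makes the tests conservative as clinics differ more. It does not inflate the error rate.

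**Step 3: patients who cannot respond.** If a share f cannot respond and is counted as not improved, the difference becomes (1−f) times the difference among the rest. Assume 20% vs 45% among those able to respond, 72 per arm, two-sided 0.05:

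| f (assumed) | Difference, all counted (points) | Power, all counted | Power, able to respond only |
|---|---|---|---|
| 0 | 25 | 90% | 90% |
| 10% | 22.5 | 85% | 87% |
| 20% | 20 | 79% | 83% |
| 30% | 17.5 | 71% | 77% |
| 40% | 15 | 63% | 71% |

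Restriction recovers about 2 to 8 points of power, because it also drops patients. Clarity is the larger gain. At f = 25%, the same data give 20% vs 45% with these patients excluded, 15% vs 34% with them counted as failures (0.75·20 and 0.75·45), and 40% vs 59% with them counted as normal at week 96 (add 25 to each).

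**The case against.** The strongest case against is that both tests are standard and legitimate, that section 6.3 offers them only in general, and that secondary findings carry no confirmatory claim. The stratified rank test is even slightly worse when clinics do not differ (72% against 74%). All of this stands, and it limits the point to efficiency.

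Several stronger readings are tempting but are not supported:
- **That baseline is ignored.** The outcomes are defined as changes from baseline. What is missing is planned adjustment for it. Selecting patients on a high NAS affects all arms alike and causes no bias.
- **That every secondary result is diluted.** The floor problem touches only ALT response and binary features without an entry minimum. Mean NAS change, HOMA, lipids, anthropometry and SF-36 have no such rule, nor does the comparison of pioglitazone with vitamin E on the primary outcome.
- **That the main histologic features are affected.** Entry requires steatosis, lobular inflammation and ballooning each to be at least 1 (section 4.2). That is on the local reading, while central scores are analysed (section 5.7), so a central 0 is possible but is the exception. The rule mainly concerns fibrosis and the minor features.
- **That the trial will count patients who cannot respond.** No denominator is stated, so this is an inference. A fall into the normal range can be read as presupposing a raised value, and the foreseen subgroup analysis shows that the issue was noticed.

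A statistical analysis plan, not at hand, may settle the denominators. The tests themselves are fixed in the protocol.

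**Conclusion.** The point holds as a loss of precision in the secondary analyses. Lack of baseline adjustment is the larger part: a variance ratio of 0.65 to 0.85 for r of 0.3 to 0.7, or 15 to 35% fewer patients for the same precision, if the linear model with equal variances is a fair proxy for the rank test. Leaving out clinic is the smaller part: about 0-2 points of power at small to moderate clinic variation and about 4-5 at large variation. The correlations, clinic variation and floor shares are all assumptions, because the protocol gives none.

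The response rules are a lesser, mainly definitional point. A reader might infer from the unstratified tests that secondary p-values are too small, but the simulations point the other way. The primary analysis and the sample size are untouched.

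**What to change.** **Section 6.3.**
- Use the clinic-stratified Mantel-Haenszel test, already chosen for the primary outcome, for the secondary binary outcomes.
- For numerical outcomes, pre-specify an ANCOVA of the week-96 value on treatment, baseline value and clinic. The linear regression on change already named there gives the same treatment estimate on the raw scale if baseline value and clinic are fixed as covariates, so the change in wording is small.
- Fix the scale (raw, log or rank) for each outcome before unmasking. Leaving it open until the distributions are seen by arm would swap one data-driven choice for another.

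**Section 6.2.**
- Report ALT response among patients with ALT above normal at baseline, and feature improvement among patients with a centrally read baseline score of at least 1.
- Give the all-patient result alongside, stating how patients who cannot respond are counted.
- Keep all patients in the numerical-change analyses.

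**Cost.** Wording only. The data are already collected, and the sample size and visits stay as they are. Some response tables will have smaller denominators.

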6.4. Missing data

The occurrence of missing data in this trial is expected to be low and, when present, is expected to be equally distributed across the 3 treatment groups. We estimate that careful selection of patients during the 6 months screening phase and the consent process should result in no more than 10% missing data from patients who drop out before completing the 96 week treatment period. In primary, intention-to-treat analyses, patients with missing data will be considered unimproved on the primary outcome measure.

The proportions with missing data will be compared across treatment groups using χ^2 tests. Nonsignificant P-values indicate that the data are missing at random (MAR). If this is the case, analyses of the non-missing data are not threatened. If the amount of missing data exceeds 10% and the data are MAR, then a variety of sensitivity analyses will be carried out to compare to the primary analysis using all available non-missing data: (1) compare pessimistic and optimistic imputations of the missing values, (2) correct for missing data using multiple imputation with 10 replicated samples, and (3) use mixed random effects logistic or linear regression models, depending on the type of outcome measure. Although unlikely in a large trial, it is possible that the missing data are not MAR and the missing data are non-ignorable. A few statistical methods are available when there are non-ignorable missing data and these would be employed; however; all such methods involve strong assumptions that cannot be verified from the available data.

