6.3. Statistical analysis

Primary hypotheses:

Statistical analyses for the two primary hypotheses will follow the intention-to-treat paradigm, which means that all randomized patients with baseline and 96 week liver biopsies will be included in the treatment group to which they were assigned. Any randomized patient who does not have the requisite biopsies will be accounted for and compared by assigned treatment group. Patients not able

to be included in the intention-to-treat analyses will be compared to those who are included with respect to demographic and other characteristics.

Since the primary outcome measure, defined in Section 6.2, is a binary indicator of improvement in histologic activity score after 96 weeks of treatment compared to baseline and since the randomization is stratified by clinic, P-values will be derived from the Mantel-Haenszel χ^2 test for stratified 2x2 tables (66). Two P-values will be derived: one comparing proportions improved in the group assigned to pioglitazone compared to the group assigned to placebo and another comparing the group assigned to vitamin E to the group assigned to placebo. Since two primary comparisons are planned, a P-value of 0.025 will be considered significant, applying a Bonferroni correction for multiple comparisons.

Given the randomized design and adequate size planned for the PIVENS trial, it is unlikely that confounding of the treatment groups by covariates related to the change in histologic activity score will occur. However, if confounding should occur, logistic regression analyses with histologic improvement as the binary response and treatment group indicator and any suspected confounders as covariates will be carried out to determine the sensitivity of the primary P-value to confounding.

Secondary hypotheses:

The first secondary hypothesis, that pioglitazone and vitamin E are equally effective in achieving histologic improvement, involves the primary outcome measure. Equivalence will be assessed in two ways: (1) a formal test for equivalence, testing that the difference between proportions improved in the pioglitazone and vitamin E groups does not exceed 10% and (2) 95% confidence intervals on the difference in proportions improved.

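### Section 6.4 reads a non-significant comparison of missingness by arm as proof of MAR, and makes the named sensitivity analyses depend on that label and on more than 10% missing

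*Protocol*

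**What the plan says.** Section 6.4 of the protocol sets out a sequence.

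- **Primary rule.** "In primary, intention-to-treat analyses, patients with missing data will be considered unimproved on the primary outcome measure".
- **Test.** "The proportions with missing data will be compared across treatment groups using χ^2 tests". No significance level is given.
- **Reading of the test.** "Nonsignificant P-values indicate that the data are missing at random (MAR").
- **Consequence.** "If this is the case, analyses of the non-missing data are not threatened".
- **Trigger for the named analyses.** "If the amount of missing data exceeds 10% and the data are MAR, then a variety of sensitivity analyses will be carried out". Three are listed: pessimistic and optimistic imputation, multiple imputation with 10 replicates, and mixed random effects models.
- **Otherwise.** "A few statistical methods are available when there are non-ignorable missing data and these would be employed". None is named, and the section adds that such methods rest on strong assumptions that the data cannot verify.

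Section 6.3 describes the intention-to-treat set differently: "all randomized patients with baseline and 96 week liver biopsies will be included in the treatment group to which they were assigned". The sentence in 6.4 that introduces the sensitivity analyses also describes the primary analysis as one of observed data only. The expected amount of missing data is 10% at most.

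**The concern.** MAR is a statement about whether missingness depends on the unseen outcome once the observed data are taken into account. Equal missing proportions by arm do not bear on this. Two arms can lose the same number of patients for opposite reasons, for example adverse effects in one and lack of benefit in the other. Nor is a non-significant P-value evidence of equal proportions when the test has little power.

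The trigger then runs the wrong way. A significant imbalance between arms is the clearest warning the test can give, yet it withdraws the analyses the protocol has specified. Pessimistic and optimistic imputation simply bounds the result and needs no MAR assumption, so there is no reason to make it wait for an MAR label. Followed as written, the plan can pronounce the observed-data analyses safe on the strength of a test that cannot show it.

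**Working it through.** **Inputs.** From Section 6.5: 80 per arm, 240 in total, placebo rate 0.14, active rate 0.40, two-sided alpha 0.025, 90% power, 10% missing. The missingness scenarios and the 0.05 level for the missingness test are assumptions, because the protocol gives neither.

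**The plan's own figure.** The printed formula, with mean rate 0.27, gives n = [2.241·√(2·0.27·0.73) + 1.282·√(0.14·0.86 + 0.40·0.60)]² / 0.26² = 70.1, so 71 per group. 71/0.90 = 78.9, so 79, which the protocol rounds to 80. It reproduces.

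**1. The test carries no outcome information.** With 12/12/12 of 80 missing, chi-square = 0 and P = 1.00 whatever happened to those 36 patients.

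Suppose a share m is missing in every arm, missing active patients are all non-responders, and missing placebo patients respond at 0.14. The observed-data active rate is 0.40/(1−m) and the observed-data placebo rate stays at 0.14. The true difference is 0.26.

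| m | Active, observed data | Difference, observed data |
|---|---|---|
| 10% | 0.444 | 0.30 |
| 15% | 0.471 | 0.33 |
| 20% | 0.500 | 0.36 |

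For comparison, counting missing as unimproved at m = 15% gives 0.40 − 0.14×0.85 = 0.40 − 0.119 = 0.281. In this scenario that rule removes most of the distortion.

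**2. Power to detect unequal missingness.** Three-arm chi-square, 80 per arm, level 0.05, by simulation (200,000 replicates):

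| True missing rates | Power |
|---|---|
| 5/10/15% | about 0.45 |
| 10/10/20% | about 0.46 |
| 7/7/15% | about 0.38 to 0.39 |

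Observed counts of 8/12/16 (36/240 = 15%) give chi-square = 3.14, P = 0.21, and would be labelled MAR.

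**3. What the trigger does.**

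| Missing per arm | Overall | P | Named analyses called for? |
|---|---|---|---|
| 8/8/17 | 33/240 = 13.8% | 0.058 | Yes |
| 8/9/18 | 35/240 = 14.6% | 0.048 | No (not MAR) |
| 3/7/12 | 22/240 = 9.2% | 0.047 | No (not MAR, and not above 10%) |

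Two more missing patients, with a wider imbalance, turn the named analyses off.

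**4. How far the primary result depends on this.** Here missing counts as unimproved, 8 are missing per arm, and the chi-square is uncorrected and unstratified (the protocol specifies a clinic-stratified Mantel-Haenszel test).

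- *At the planned rates.* 72 completers per arm give 0.40×72 ≈ 29 and 0.14×72 ≈ 10 improved. 29/80 vs 10/80: P = 0.0005. If 6 of the 8 missing placebo patients and no missing active patients had improved, 29 vs 16: P = 0.022. With 7 of 8, 29 vs 17: P = 0.036, above 0.025.
- *A chosen near-threshold case.* 28/80 vs 13/80: P = 0.0066. With 3 of 8 missing placebo patients improved, 28 vs 16: P = 0.034. With all 8, 28 vs 21: P = 0.23. If one missing active patient also improved, 29 vs 16: P = 0.022, significant again.

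**The case against.** The strongest defence is that the primary analysis does not use MAR: missing patients count as failures, so the false sentence concerns only analyses of observed data. This stands in part. If that rule governs, the primary result is largely shielded, as steps 1 and 4 show. But Section 6.3 and the later wording of 6.4 point to an observed-data analysis, and the rule is worded for the primary outcome only, so it does not reach the secondary outcomes.

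A reader might infer that sensitivity analysis is simply skipped whenever the test is significant. The protocol does not say that. It commits to methods for non-ignorable missingness in that case. The defect is that specified analyses give way to an unnamed promise.

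A reader might also infer that the primary result is fragile and would go out unchecked. The documents do not support this. The 28 vs 13 example is a constructed near-threshold result. At the planned effect, 7 of 8 missing placebo patients and none of the missing active patients would have to have improved before significance is lost. Nothing in the protocol forbids sensitivity analyses at 10% missing or less, and Section 6.3 also requires patients without biopsies to be compared by arm, and with those included. That comparison is descriptive and does not rescue the MAR inference.

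Finally, multiple imputation and mixed models do usually assume MAR, so tying them to MAR has some logic. That logic fails when MAR is declared by a test that cannot establish it, and it never applied to the pessimistic and optimistic bounds. The choice of imputation predictors is detail for the SAP and no part of this point.

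**Conclusion.** The point holds as a rule that is wrong as written, and it should be fixed. A non-significant chi-square by arm cannot show MAR and does not make observed-data analyses safe. The two-part trigger withholds the named analyses when missingness differs significantly by arm.

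The exposure falls on observed-data and secondary analyses. The bias of 0.07 (0.33 against 0.26) rests on an assumed 15% missing in every arm with every missing active patient a non-responder; it is 0.04 at 10% missing and 0.10 at 20%. The power figures rest on the assumed missing rates and 0.05 level. The effect on the primary result is limited if missing-as-unimproved governs, and larger if the observed-data wording does.

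**What to change.** In Section 6.4:

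1. Delete the sentence that reads a non-significant P-value as MAR, and the one that declares observed-data analyses unthreatened.
2. Keep missingness by arm, with reasons, as description only.
3. Run the analyses already named (pessimistic and optimistic imputation, multiple imputation, mixed models) whatever the test result and whatever the amount missing.
4. Name a tipping-point table as the analysis for non-ignorable missingness, in place of the general promise.

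Imputation-model details can stay with the SAP. The cost is a wording change and a few hours of programming. Design and sample size are unaffected.
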